#### 1.2.4. Known and Potential Risks and Benefits

Twenty three clinical trials, including four Phase III, four Phase II, and fifteen Phase I studies have been completed to date, in which 3042 subjects were exposed to oritavancin. The most common adverse events (>3%) by preferred term in either treatment group, in the SOLO I or SOLO II studies were nausea, headache, vomiting, cellulitis, diarrhea, constipation, infusion site extravasation, pyrexia and pruritus, as outlined in Table 4.

Serious hypersensitivity reactions have been reported with the use of oritavancin. If an acute hypersensitivity reaction occurs during oritavancin infusion, discontinue oritavancin immediately and institute appropriate supportive care. Due to the possibility of cross-sensitivity, carefully monitor for signs of hypersensitivity during ORBACTIV infusion in patients with a history of glycopeptide allergy. In the Phase III ABSSSI clinical trials, the median onset of hypersensitivity reactions in oritavancin -treated patients was 1.2 days and the median duration of these reactions was 2.4 days.

Infusion related reactions or anaphylactoid reactions have been reported with oritavancin including pruritus, urticaria or flushing. If reactions do occur, slowing or interrupting the infusion should be considered to mitigate the reaction.

Oritavancin is a mild inhibitor of Cytochrome P450 2C9 enzyme (CYP2C9), and therefore, has the potential to increase warfarin concentrations when administered concomitantly. Oritavancin has been shown to artificially prolong PT and INR for up to 24 hours, making the monitoring of the anticoagulation effect of warfarin unreliable up to 24 hours after an oritavancin dose. Subjects

who are on warfarin (including all subjects in this trial) should be closely monitored for signs of bleeding.

A complete description of relevant risks of oritavancin can be found in the investigator's brochure [Oritavancin Investigator's Brochure Version 10] and the United States Package Insert (USPI).

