# 10.3.3.2. Clinical Safety Laboratory Tests

Clinical safety laboratory values and changes from Baseline, including prothrombin time (PT)/international normalized ratio (INR), direct and indirect Coombs, Immunoglobulin panel, oritavancin antibody assay, will be summarized descriptively. Clinically significant (CS) values will also be flagged in a listing.

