8.2 Clinical Laboratory Assessments

Clinical safety laboratory values and changes from baseline of hematology, serum chemistry, and urinalysis, including prothrombin time (PT)/international normalized ratio (INR), direct and indirect Coombs (DAT and IAT), Immunoglobulin panel, oritavancin antibody assay, will be summarized descriptively. Potentially clinically significant (PCS) values will also be flagged in a listing. The criteria for potentially clinical significant liver function tests are displayed in [Table 2](#).

Unscheduled assessments that are not used for baseline will not be included in summary tables; however, all measurements will be listed.

Table 2: Criteria for Potential Clinically Significant Abnormal Lab Tests

Parameter	Lower limit	Upper limit
Hematology		
Red Blood Cell Count	$\leq 0.75 \times \text{LLN}$	$\geq 1.25 \times \text{ULN}$
WBC's Count	$< 2.0 \times 10^9/\text{L}$	
Hematocrit	$\leq 0.75 \times \text{LLN}$	$\geq 1.25 \times \text{ULN}$
Hemoglobin	$\leq 11.5 \text{ g/dL}$ Male	$\geq 18.0 \text{ g/dL}$ Male
	$\leq 9.5 \text{ g/dL}$ Female	$\geq 16.0 \text{ g/dL}$ Female
Platelet count	$\leq 75 \times 10^9/\text{L}$	$\geq 700 \times 10^9/\text{L}$
Serum Chemistry		
BUN		$\geq 10.7 \text{ mmol/L}$
Calcium	$\leq 7.0 \text{ mg/dL}$	$\geq 15.5 \text{ mg/dL}$
Creatinine		$\geq 2.0 \text{ mg/dL}$
Glucose	$\leq 50 \text{ mg/dL}$	$\geq 180 \text{ mg/dL}$
Potassium	$\leq 3.0 \text{ mmol/L}$	$\geq 5.5 \text{ mmol/L}$
Sodium	$\leq 125 \text{ mmol/L}$	$\geq 150 \text{ mmol/L}$
Liver Function Tests (LFTs)		
Alanine Transaminase (ALT/SGPT) $\geq 3x, 5x, 10x$ and $20x \text{ ULN}$		
Aspartate Transaminase (AST/SGOT) $\geq 3x, 5x, 10x$ and $20x \text{ ULN}$		
ALT or AST $\geq 3x, 5x, 10x$, or $20x \text{ ULN}$		
Total bilirubin $\geq 1.5x$ and $2x \text{ ULN}$		
Alkaline Phosphatase (ALP) $\geq 1.5x$ and $3x \text{ ULN}$		
ALT/AST $\geq 3x \text{ ULN}$ and Total bilirubin $\geq 2x \text{ ULN}$;		
Potential Hy's Law cases: ALT or AST $\geq 3 \times \text{ULN}$, Total bilirubin $\geq 2 \times \text{ULN}$, and ALP $\leq 2 \times \text{ULN}$		

LLN: lower limit of the standard reference (normal) range.

ULN: upper limit of the standard reference (normal) range.

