8.3 Vital Signs

Vital sign measurements and changes from baseline will be summarized descriptively at each scheduled timepoint. Potentially clinically significant changes will also be flagged in a listing based on the following thresholds:

- Respiratory Rate \leq 10 rpm;
- Respiratory Rate \geq 30 rpm;
- Systolic blood pressure \geq 180 mm Hg and increase \geq 20 mm Hg from Baseline;
- Diastolic blood pressure \geq 110 mm Hg and increase \geq 15 mm Hg from Baseline;
- Systolic blood pressure \leq 90 mm Hg and decrease \geq 20 mm Hg from Baseline;
- Diastolic blood pressure \leq 50 mm Hg and decrease \geq 15 mm Hg from Baseline;
- Heart rate \geq 120 bpm with increase \geq 15 bpm from Baseline;
- Heart Rate \leq 50 bpm with decrease \geq 15 bpm from Baseline.

Unscheduled assessments that are not used for baseline will not be included in summary tables; however, all measurements will be listed.

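### SAP Table 2 flags low hemoglobin by level only, so a 3 g/dL fall can go unflagged and subjects with large falls are not counted

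*SAP*

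**What the plan says.** SAP 8.2 states that "Potentially clinically significant (PCS) values will also be flagged in a listing". What is flagged is the value, not its change. The low hemoglobin limits in Table 2 are "\leq 11.5 \text{ g/dL}$ Male" and "\leq 9.5 \text{ g/dL}$ Female". The high limits are "\geq 18.0 \text{ g/dL}$ Male" and "\geq 16.0 \text{ g/dL}$ Female". Hematocrit and red blood cell count are flagged at 0.75 times the lower, or 1.25 times the upper, limit of normal, again without reference to baseline. The sentence introducing Table 2 mentions only liver function tests, but the table's title and rows cover hematology and chemistry, so the hemoglobin limits apply.

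Protocol 10.3.3.2 has a parallel sentence, "Clinically significant (CS) values will also be flagged in a listing", and gives no criterion. Neither document adds a change-based hemoglobin flag, a shift table or a count of subjects with a given fall.

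Other parts of the plan bear on the point:

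- SAP 8.2 summarises hematology changes from baseline, and SAP 4 includes the minimum and maximum among the statistics shown.
- SAP 8.2 keeps unscheduled measurements not used as baseline out of the summary tables, but lists them.
- The schedule of events places hematology at screening, Day 7 and Day 14.
- Protocol 1.2.4 says that subjects on warfarin "should be closely monitored for signs of bleeding".
- SAP 2.3.1 makes laboratory abnormalities one component of the primary endpoint.

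**The concern.** A fall in hemoglobin is the ordinary laboratory trace of blood loss, and it is measured against the subject's own baseline. A fixed level answers a different question: whether the subject is now below a threshold. A subject who starts well above the threshold can lose a good deal before reaching it.

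At stake is the completeness of one component of the primary safety endpoint. Those reading the study report will want to know how many subjects on warfarin had a material fall after oritavancin, who they were, and what their INR and adverse events looked like at the time. As planned, the flag does not answer that and no table gives the count.

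**Working it through.** The plan has no figure to reproduce: the 25 warfarin subjects rest on feasibility and clinical judgment (SAP 3.2). The check applies the Table 2 rule as written.

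**Inputs from the documents.** Lower limits L = 11.5 (male) and 9.5 (female) g/dL; upper limits 18.0 and 16.0 g/dL; 25 warfarin subjects.

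**Assumptions.** Hemoglobin is reported to 0.1 g/dL. The baselines below are illustrative; the documents give none.

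**Step 1: the rule.** A low value H is flagged if H ≤ L. From baseline B, the largest unflagged fall is B − (L + 0.1).

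| Sex | Baseline | 3.0 g/dL fall to | Flagged? | Largest unflagged fall |
|---|---|---|---|---|
| Male | 15.0 | 12.0 | No (12.0 > 11.5) | 15.0 − 11.6 = 3.4 |
| Male | 16.0 | 13.0 | No (13.0 > 11.5) | 16.0 − 11.6 = 4.4 |
| Female | 13.0 | 10.0 | No (10.0 > 9.5) | 13.0 − 9.6 = 3.4 |
| Female | 14.0 | 11.0 | No (11.0 > 9.5) | 14.0 − 9.6 = 4.4 |

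The ceiling, from the highest baseline not itself flagged, is 17.9 − 11.6 = 6.3 g/dL in men and 15.9 − 9.6 = 6.3 g/dL in women.

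**Step 2: who is affected.** A fall of exactly c goes unflagged when B ≥ L + 0.1 + c.

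| c (g/dL) | Male baseline at or above | Female baseline at or above |
|---|---|---|
| 1.5 | 11.6 + 1.5 = 13.1 | 9.6 + 1.5 = 11.1 |
| 2.0 | 11.6 + 2.0 = 13.6 | 9.6 + 2.0 = 11.6 |
| 3.0 | 11.6 + 3.0 = 14.6 | 9.6 + 3.0 = 12.6 |

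Below these baselines the existing limit already catches the fall.

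**Step 3: do the other rows catch it?** The lower limits of normal are not in the documents, so ranges are assumed.

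- Hematocrit, with hemoglobin taken as hematocrit/3. Male lower limit 38–41%: 0.75 × 38 = 28.5% to 0.75 × 41 = 30.75%, or hemoglobin of about 9.5–10.25 g/dL. Female 34–37%: 25.5–27.75%, or about 8.5–9.25 g/dL.
- Red cell count, with 28–32 pg hemoglobin per cell. Male lower limit 4.2–4.5 × 10¹²/L: 3.15–3.375, or about 8.8–10.8 g/dL. Female 3.8–4.0: 2.85–3.0, or about 8.0–9.6 g/dL.

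All of these lie below the 12.0 and 10.0 g/dL in the two examples, so neither row would flag them. Table 2 has no PT/INR row either.

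**Step 4: what the planned summary gives.** If all 25 subjects have a Day 7 value and one falls by 3.0 g/dL, the minimum change is −3.0 or lower, so the extreme is visible. The number of such subjects is not. Since 0.25 × 25 = 6.25, the lower quartile is the 7th smallest change (taking the next whole rank). Anywhere from one to six subjects could therefore have fallen by 2 g/dL or more with the same minimum and a lower quartile still above −2.0. A hemoglobin drawn between visits for suspected bleeding enters none of these statistics.

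**The case against.** The strongest reply is that the report has other routes to the same information. The minimum change exposes the worst scheduled fall, and the full listing lets a reader find the subject. Adverse events are assessed at every visit in the schedule, and the protocol's definition (8.1.1) admits an abnormal laboratory finding. Protocol 7.2.4 has clinically significant laboratory findings followed to resolution. Nothing in either document makes the flagged listing the means of detecting bleeding; the sentence in Protocol 1.2.4 concerns clinical monitoring and does not mention hemoglobin. The study is descriptive, and no planned estimate is wrong. All of this stands, and it limits the weight of the point. It does not supply the count, and it leaves unscheduled values in the listing alone.

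A reader might infer more in three ways that the documents do not support:

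- *That a single fall is lost in the group mean* (3.0/25 = 0.12 g/dL). SAP 4 also reports the minimum, so it is not lost.
- *That the vital-sign rules in SAP 8.3 are a precedent.* They require level and change together, as in "Systolic blood pressure \leq 90 mm Hg and decrease \geq 20 mm Hg from Baseline". That form with the present hemoglobin limits would still pass over 15.0 to 12.0 g/dL.
- *That flagging a subject with a stable low value is a defect to correct here.* A fixed limit will do that, and the change proposed below leaves it so.

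**Conclusion.** The point holds in a limited form. Table 2 identifies low hemoglobin by level alone, and a fall of 3.0 g/dL can go unflagged from ordinary-looking baselines (ceiling 6.3 g/dL from an unflagged baseline). The planned displays show the largest scheduled fall but not how many subjects had a large one, and they omit unscheduled values from the tables.

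A reader might infer that the plan would miss bleeding altogether. It would not: the data are collected and listed, and recognised bleeding is reported as an adverse event. The size is that of a cheap improvement of minor severity.

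The conclusion on flagging rests only on the Table 2 limits and reporting to 0.1 g/dL. The finding that hematocrit and red cell count do not help in the two examples rests on the assumed reference ranges and conversions. The documents do not say how often such falls would occur, so no expected number of missed flags is claimed.

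**What to change.** In SAP 8.2:

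- Keep the present hemoglobin limits and add a separate Table 2 criterion for decrease from baseline, standing on its own and not conditional on level.
- Have the sponsor choose the cut-off and fix it before database lock. As an assumed illustration, 2 g/dL would flag both examples; 1.5 to 3 g/dL is the range to consider. One pre-specified value is enough.
- Apply it to scheduled and unscheduled post-dose values.
- Report the number of subjects meeting it by cohort, under the SAP 4 rule that cohorts of 4 or fewer are listed only.
- In the listing, show each flagged subject's adverse events and INR values alongside. Showing all adverse events avoids having to define a bleeding category.

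State that this is an analysis flag and sets no clinical rule.

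The cost is one row in Table 2, one count, one listing column and some programming to bring adverse events and INR together. No new data are collected. The downside is a few extra flags to review, some from causes other than bleeding.

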8.3 Vital Signs

Vital sign measurements and changes from baseline will be summarized descriptively at each scheduled timepoint. Potentially clinically significant changes will also be flagged in a listing based on the following thresholds:

- Respiratory Rate \leq 10 rpm;
- Respiratory Rate \geq 30 rpm;
- Systolic blood pressure \geq 180 mm Hg and increase \geq 20 mm Hg from Baseline;
- Diastolic blood pressure \geq 110 mm Hg and increase \geq 15 mm Hg from Baseline;
- Systolic blood pressure \leq 90 mm Hg and decrease \geq 20 mm Hg from Baseline;
- Diastolic blood pressure \leq 50 mm Hg and decrease \geq 15 mm Hg from Baseline;
- Heart rate \geq 120 bpm with increase \geq 15 bpm from Baseline;
- Heart Rate \leq 50 bpm with decrease \geq 15 bpm from Baseline.

Unscheduled assessments that are not used for baseline will not be included in summary tables; however, all measurements will be listed.

8.4 Extent of Exposure

Study drug administration dates and times will be provided in a data listing.

9 PHARMACOKINETIC ANALYSES

Not applicable as no pharmacokinetic sample was collected.

10 EXPLORATORY ANALYSIS

No exploratory analysis is planned.

